Digit Symbol Substitution Task (DSST): The Digit Symbol Substitution Task is a well-established psychometric test paradigm that is used to measure general cognitive performance. Participants must match symbols to digits and press the key that corresponds to the digit. The test is designed as a continuous performance task in which the participant must accomplish as many as possible correct matches within the 1.5 minute test period. The DSST results will be assessed for number of correct matches, and speed of completion for the entire set of a subset of the symbols.

Karolinska Sleepiness Scale (KSS): The Karolinska Sleepiness Scale measures subjective levels of fatigue. KSS queries subjects as to how sleepy they feel at that moment. The subjects answer is based on a 9-point scale where 1 = extremely awake and 9 = extremely sleepy/fighting to stay awake.

Matrix Reasoning Task (MRT): The MRT is a measure of abstract reasoning and consists of increasingly difficult pattern matching tasks. It is analogous to Raven's Progressive Matrices and recruits prefrontal, parietal, and temporal cortices. It is based on a well-known measure of the "g" factor. The test consists of a series of patterns, overlaid on a grid. One element from the grid is missing and the participant must select the element that fits the pattern from a set of alternative options. The current implementation uses 12 consecutive stimuli. MRT administration will stop automatically if three consecutive stimuli are answered incorrectly.

Paired Associates Learning task (PAL): The Paired Associates Learning Task is a well-established cognitive task used to assess declarative memory. Participants are presented with word pairs to learn. Immediately following and again in the morning after they wake up they are tested on the recall of the words. The recall testing involves showing participants one word and they are asked to state the paired word that they learned previously. Overnight memory retention is determined by the difference in the number of recalled words between morning retrieval testing after sleep and immediate recall performance at learning before sleep. The testing is scored by a technician and may also be recorded for scoring confirmation.

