As a second test condition of this protocol, we will also utilize a different system, Phase Locked Loop (Prototype 2) to provide acoustic stimulation during sleep. This Phase locked Loop (PLL) system was developed at Northwestern University and functions similarly to the PowerSleep Prototype 1, but the stimulation will be provided using a standard PC setup at the bedside using standard polysomnography (PSG) electrodes and acoustic stimuli will be delivered through earphones at specified times during sleep to increase slow wave activity.

II. SPECIFIC AIMS/HYPOTHESES

Primary Aim:

The primary aim of this study is to assess the effects of the auditory stimulation delivered by both the PowerSleep systems (Prototype 1) and a system developed

by Northwestern University (Prototype 2) in adults with mildly sleep restricted schedules.

We hypothesize that one night of in-lab use of a PowerSleep system (Prototype 1) or Prototype 2 under an active condition (tones played to increase slow-wave activity), as compared to one night of in-lab use of the same PowerSleep system (prototype 1) or Prototype 2 under a sham condition (no tones played) will result in a significant increase ($\geq 5\%$) in cumulative or average slow-wave activity (SWA) in nonREM sleep across the whole night of sleep compared to sham. NOTE: We will also compare the relative ability of Prototype 1 versus Prototype 2 to increase the magnitude of SWA in sleep.

Secondary Aim:

The secondary aim of the study is to assess the impact of active versus sham PowerSleep Prototype 1 and Prototype 2 systems on measures of daytime function (PAL and PVT-B). The estimated effect of PowerSleep on specific measure(s) of daytime function will be used to help inform the choice of outcomes for future studies.

Exploratory endpoints:

Exploratory endpoints will include analysis of other daytime outcome assessments in relation to SWA.

III. STUDY DESIGN AND METHODS

- A. Design:** This study is a randomized, single-blind, sham-controlled pilot cross-over trial comparing the feasibility, and efficacy of 2 nights of in lab use with active versus sham conditions in adults with sleep restricted schedules. The expected duration of the study for each participant is up to 5 weeks.

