Participants will drop off or mail their actigraph and sleep log to the Center for Circadian and Sleep Medicine for review by the study staff. The actigraph data will be reviewed by a trained technologist. Only participants that demonstrate a regular sleep schedule and an average sleep duration of 6-7 hours during the work week will be asked to return to the lab for the study. A regular sleep schedule will be defined as a bedtime between 9pm and midnight with no more than 1 hour of variability across the 7 nights. Qualifying participants will be asked to continue wearing the actiwatch and completing the sleep diary throughout the remainder of the study.

Visit 2 Procedures (3 days/2 nights with washout in between nights):

Participants will be randomly assigned to the sham or active stimulation condition during the first night of the overnight visits, and the other condition (sham or active stimulation) during the second night of the overnight visits. Participants may also be asked to undergo additional night study testing if data collected is unable to be analyzed due to unforeseen technical or environmental reasons. Participants and study staff will be blinded to the condition they are receiving during each overnight study for prototype 1. However, study staff will not be blinded during each overnight for prototype 2.

Active condition: Participants will be set-up with one of the PowerSleep Prototypes. Soft audio tones (below 65dB to prevent arousals from sleep) will be administered via the headphones during deep sleep throughout the night.

Sham condition: Participants will be set up with the same PowerSleep prototype as with the active arm, however no audio tones will be played.

Participants will typically be asked to arrive at the Sleep Disorders Center on the 7th Floor of Arkes or Galter Pavilion ~3 hours before their usual bedtime.

Upon arriving at the Sleep Disorders Center for the first overnight study, the actigraph data will be downloaded for review by a trained technologist. Only participants that demonstrate a regular sleep schedule and a sleep duration of 6-7 hours per night will be asked to remain in the study and through completion.

The PAL learning set will be completed before the participant goes to bed.

Overnight monitoring:

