The subject will be allowed to go home or to work during the day and will be instructed not to nap during the day. This will be monitored with the actigraph. The subject will return to the lab the following evening 3 hours before the usual bedtime and will be instrumented and studied as described for night 1. For example, participants that spent the night Monday and completed Tuesday morning testing will come into the lab Wednesday night for Thursday morning testing or if participants spent Tuesday night and completed Wednesday morning testing they will come into the lab Thursday night for Friday morning testing.

Visit 4 Procedures (3 days/2 nights):

Participants will return to the Sleep Disorders Center to complete the second set of overnight studies one or two weeks after the first set of overnight studies. If participants spent Monday and Wednesday night in the lab for the first set of overnight studies, they will complete the second set of overnight visits Monday and Wednesday. The actigraph data will be similarly downloaded and reviewed for further participation upon arriving at the Sleep Disorders Center. This visit will be identical to Visit 3 except that the subjects will receive the prototype system that was not used in Visit 3 (Prototype 1 or 2).

V. STATISTICAL ANALYSIS

Determination of Sample Size

Twelve participants will be enrolled in order to ensure ten completed data sets. Since this is a pilot study, no sample-size calculation was performed.

General Considerations

The primary analysis will be performed including all completed participants. Subjects who complete all 4 in lab study nights with functional devices will be included in data analysis. If the sleep data are not usable for one or more of the participants' treatment conditions, those participants will be excluded from the primary analysis, and site(s) may over-enroll to compensate for these missing data. The analysis of safety will include all randomized subjects.

All variables will be summarized by descriptive statistics. The statistics for continuous variables includes mean, median, standard deviation, minimum, maximum, 95% confidence interval (CI) for the mean, and number of observations. For categorical variables, number and percentage of subjects with the event will be presented. Continuous variables will be summarized using the number of non-missing observations,

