mean, standard deviation (SD), 95% confidence interval (CI) for the mean, median, minimum, and maximum; categorical variables will be summarized using the frequency count and the percentage of subjects in each category. All analyses will be conducted using either SPSS® or SAS® software.

There are no statistical criteria for terminating the study. No sensitivity analysis will be completed, and any deviations to the original statistical plan will be noted in the analysis report.

Philips Respironics will complete the data analysis on Prototype 1. In addition Philips Respironics will analyze the Prototype 2 data in the same manner.

Subject Disposition

Subject disposition, including the total number of participants enrolled, randomized, completed, early terminations and withdrawals, will be presented by treatment group, and overall. In addition, a listing will be provided with the reasons for discontinuation by treatment group.

Demographics and Baseline Characteristics

Standard subject demographics (e.g., age and gender) and baseline characteristics will be summarized for all participants enrolled and for evaluable subjects.

Treatment Compliance

It is expected that the drop-out rate will be low as the study is of short duration and will be completed in a controlled, in-lab setting.

Primary Efficacy Analysis

The primary efficacy measure for this study is the cumulative or average slow-wave activity (SWA).

The primary analysis will be done on completed participants with SWA data collected during the four conditions: Prototype 1 active and sham, Prototype 2 active and sham. A 2-way repeated measures Analysis of Variance (RMANOVA) will examine the SWA data with the repeated measures factors of therapy (active and sham) and prototype (1 and 2). An interaction factor will also be included to determine whether the active / sham effect differs between prototypes. The significance level will be $p < 0.05$.

If the required assumptions for the RMANOVA model are violated, transformation of the data or non-parametric procedures may be used.

Secondary Efficacy Analysis

The daytime outcomes will be analyzed using the same statistical model as the SWA data.

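### PAL retention is analysed as a raw morning-minus-evening difference, which fixes the slope on pre-sleep recall at 1 and may cost precision in a secondary estimate meant to guide later outcome choice

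*Combined protocol and SAP*

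**What the plan says.** The definition of the Paired Associates Learning task describes two recall tests per learning set: "Immediately following and again in the morning after they wake up they are tested on the recall of the words". It then defines the score: "Overnight memory retention is determined by the difference in the number of recalled words between morning retrieval testing after sleep and immediate recall performance". No other PAL retention measure is defined.

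On timing, the procedures for the first set of overnight nights (headed Visit 2 Procedures) state: "The PAL learning set will be completed before the participant goes to bed". For the second night of that set the participant "will be instrumented and studied as described for night 1". Visit 4 Procedures adds: "This visit will be identical to Visit 3", apart from the switch of prototype. I read Visit 3 there as the first overnight set. Each completer therefore has four pre-sleep recall scores, each taken before that night's tones or sham.

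On analysis, Secondary Efficacy Analysis says: "The daytime outcomes will be analyzed using the same statistical model as the SWA data". Primary Efficacy Analysis gives that model as a two-way repeated-measures ANOVA with "repeated measures factors of therapy (active and sham) and prototype (1 and 2"), plus their interaction. It names no covariate. General Considerations rules out sensitivity analyses, so no other PAL analysis is planned.

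**The concern.** A difference score is a baseline adjustment with the slope set to exactly 1. If morning recall moves by less than one word per word of evening recall within a person, the difference over-corrects, and part of the night-to-night variation in evening recall passes into the outcome. Estimating the slope removes that part.

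PAL is one of only two daytime measures named in the Secondary Aim. The same aim says the estimated effects will help choose outcomes for future studies. With ten completers, precision largely decides how useful that estimate is, and a noisier score could make a responsive measure look unresponsive.

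**Working it through.** **Inputs from the documents.** Ten completed data sets (Determination of Sample Size); four nights each; significance level 0.05, taken as two-sided. No PAL SD, correlation, effect size or power is given, so there is no figure of the plan to reproduce.

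**Assumptions.** Within-person, night-level correlation r between evening and morning recall of 0.3 to 0.9. Equal evening and morning within-person SD s, except in step 3. No carry-over into later evening scores. For power, a therapy effect of 0.7 s. Only night-level correlation matters, because stable differences between people cancel in the crossover.

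**Step 1: large-sample variance.**
- Difference score: s²(1 + 1 − 2r) = 2s²(1 − r).
- Morning recall adjusted for evening recall: s²(1 − r²).
- Ratio, adjusted to difference: (1 − r²) / [2(1 − r)] = (1 + r)/2.

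**Step 2: cost of estimating the slope.** Ten participants by four nights give 40 values. Removing 10 participant means and 3 condition contrasts leaves 27 degrees of freedom. One slope pooled over these inflates the variance by 1 + 1/25 = 1.04.

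The planned ANOVA tests therapy against participant-by-therapy variation on 9 degrees of freedom. The power columns compare that test with the adjusted mixed model that keeps this error term. The last three columns are simulated with a common therapy effect in all participants.

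| r | (1+r)/2 | × 1.04 | Simulated variance ratio | Power, planned ANOVA | Power, adjusted |
|---|---|---|---|---|---|
| 0.3 | 0.65 | 0.68 | 0.69 | about 38% | about 53% |
| 0.5 | 0.75 | 0.78 | 0.78 | about 49% | about 61% |
| 0.7 | 0.85 | 0.88 | 0.88 | about 73% | about 80% |
| 0.8 | 0.90 | 0.94 | 0.96 | about 87% | little change |
| 0.9 | 0.95 | 0.99 | 1.00 | about 99% | no material change |

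**Step 3: unequal SDs.** Let k be the morning SD divided by the evening SD. The true slope is rk, and the ratio is k²(1 − r²) / (k² + 1 − 2rk).
- k = 1.25, r = 0.8: slope 1.00; ratio 0.5625/0.5625 = 1.00; times 1.04 gives 1.04, a 4% loss.
- k = 0.8, r = 0.8: slope 0.64; ratio 0.2304/0.36 = 0.64; times 1.04 gives 0.67.

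A high r alone therefore does not settle the question. What matters is how far the slope is from 1.

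**Step 4: response that varies between people.** If the therapy effect has between-person SD τ (in units of s), both estimators gain τ² and the ratio moves towards 1. With τ = 0.5 assumed, so τ² = 0.25:
- r = 0.3: (0.91 × 1.04 + 0.25)/(1.40 + 0.25) = 0.73.
- r = 0.5: (0.75 × 1.04 + 0.25)/(1.00 + 0.25) = 0.82.
- r = 0.7: (0.51 × 1.04 + 0.25)/(0.60 + 0.25) = 0.92.

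**Step 5: which adjusted model.** Simulated type I error with τ = 0.5 and a mean effect of zero:
- Planned ANOVA on the difference: 4.6% to 5.3%.
- Participant fixed effects with a single residual: 7.0%, 8.2%, 9.0% and 11.7% at r of 0.5, 0.7, 0.8 and 0.9.
- One pooled slope with the participant-by-therapy error term kept: about 5% to 6.5%.

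If the slope is instead estimated only within the therapy contrast, its cost is 1 + 1/7, and the variance gain is gone at r = 2/(8/7) − 1 = 0.75.

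**The case against.** The strongest reply is that nothing here is wrong. The difference already adjusts for evening recall, words kept or lost overnight is the construct of interest and easy to interpret, and the therapy contrast is unbiased. That stands. A reader might infer that the plan ignores the baseline or that the memory result will be biased; the documents support neither.

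A second reply is that the size rests wholly on assumed values. Evening and morning tests use the same word pairs, so r may be high, and the gain is then small unless the SDs also differ. This stands too. It rules out saying that the score does carry avoidable noise; it may.

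A third is that a careless fix can do harm. A reader might add the covariate in a linear model with participant as a fixed effect and one residual, and find larger power. Part of that comes from replacing a 9-df error term with a pooled one, which assumes that everyone responds alike. The Background gives reason for doubt: in the earlier in-lab study 18 of 24 participants had any SWA increase, and its size tracked the improvement in executive function. Step 5 shows the cost in false positives. This objection governs the choice of model but does not remove the point.

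Finally, the stakes are modest: a secondary outcome in a pilot with no sample-size calculation, whose estimate informs a later choice and is not a formal gate.

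**Conclusion.** The point holds as a modest and conditional matter of precision. The plan fixes at 1 a slope that it could estimate from data already collected. With ten completers, equal SDs and a common response to therapy, estimating it would lower the variance of the PAL therapy effect by about 31%, 22% and 12% at r of 0.3, 0.5 and 0.7, and by little or nothing at 0.8 to 0.9. If the true slope is 1, about 4% is lost. If response varies between people, the gain shrinks. The documents give none of r, the SDs or the response variation, so where this trial falls in that range is unknown. The case for the change is the asymmetry: a loss of a few percent at worst, against a gain of up to about a third over the range examined.

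**What to change.** Add to Secondary Efficacy Analysis that PAL will be analysed as morning recall (or, with the same therapy effect, the difference) in a linear mixed model with:
- therapy, prototype and their interaction;
- the same night's pre-sleep recall, centred on the participant's own mean, with one slope pooled over the four nights;
- random participant, participant-by-therapy and participant-by-prototype effects.

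Report the raw morning-minus-evening difference descriptively. Fix this before the data are seen, so that there is no later choice between two PAL scores.

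The cost is one estimated slope, a mixed model (available in SAS or SPSS, which the plan already names) in place of a plain ANOVA table, and a small possible loss if the slope is near 1. No new data are needed. Make no general claim that type I error stays at 5%: the participant-by-therapy term is needed to keep it near that level, and even with it the simulated rate was about 5% to 6.5%.

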Polysomnography (PSG): Continuous and simultaneous recording of physiological variables during sleep, i.e., EEG, EOG, EMG (the three basic stage scoring parameters), EKG, respiratory air flow, respiratory excursion, lower limb movement, and other electrophysiological variables will be used to record sleep during all admissions for subjects. EEG as recorded by the Powersleep device or the standard PSG EEG channels

will also be analyzed for slow wave activity; a measure of the frequency and amplitude of slow waves.

PowerSleep Prototype 1: A wearable and non-invasive device, consisting of a headband with 2 electrodes (one forehead and one mastoid) and speakers located in the headband over each ear. The headband is adjusted via an adjustable slider. The device also includes a right mastoid reference electrode. EEG will be recorded by the PowerSleep device. Soft audio tones (below 65dB) will be administered via the speakers system during deep sleep as determined by the functionality of the device. This PowerSleep device has been extensively studied, and is a released product available for sale. The low risk PowerSleep device does not require a 510(k) and is considered a general wellness medical device.

Prototype 2: The PLL set up will function similarly to the PowerSleep prototype 1, but the stimulation will be provided using a standard PC setup at the bedside using standard PSG electrodes. EEG will be monitored and SWS identified using a standard PSG channels (international 10-20 system: Fpz, F3, F4, C3, C4, P3, P4, O1, O2) referenced to left mastoid. Electro-oculogram (EOG) will be recorded using 2 electrodes placed lateral to each eye and chin electromyogram (EMG) was recorded using 3 chin electrodes. The full EEG data set will be collected using Brain Vision Recorder software (Brain Products GmbH) and stored for off-line analysis and sleep scoring. A Matlab script (R2014b, MathWorks, Natick, MA) was developed for online detection of slow-waves and to control acoustic stimulation in a phase-locked manner (targeting the up phase of the slow wave) as described previously (Santostasi et al., 2016). Acoustic stimulation provided by headphones with an audible soft volume that do not result in arousals will be used. This device has been studied, however, is not a released product and therefore considered investigational.

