In addition, results (N=24) from an in-lab study conducted by the Cooperative Research Centre (CRC) for Alertness, Safety and Productivity with the PowerSleep device, showed positive results with SWA and executive function (verbal fluency task). An automated device based on the acoustic enhancement of slow wave sleep increased slow wave activity at the group level. In the majority of individuals, 18/24 75% (> 0% increase), 15/24 62.5% (> 5% increase). No change in cognitive outcomes was observed at the group level. At the individual level, the majority of individuals (75%) had increased slow wave activity. Magnitude of SWA increase was associated with the magnitude of improvement in executive function.

PowerSleep is a non-invasive portable light weight device designed to stimulate deep slow-wave sleep and thereby reduce daytime sleepiness associated with insufficient sleep. The concept is to stimulate deep sleep also known as Slow-Wave Sleep (SWS), to compensate for insufficient sleep duration by increasing sleep intensity. Sleep intensity can be objectively assessed by Slow-Wave Activity (SWA), defined as EEG spectral power in the frequency range 0.5-4 Hz. In normal individuals, a reduction in the amounts of SWA consistently results in reduced alertness with impaired performance due to cognitive and memory deficits.

The PowerSleep device delivers acoustic stimuli that are calibrated to stimulate SWA without awakening the user. The PowerSleep device is wearable and non-invasive, consisting of a headband with 1 integrated electrode, one mastoid reference electrode, and speakers located in the headband over each ear. The headband is adjusted via an adjustable slider. The device monitors and records EEG throughout the night, and is capable of on-line identification of sleep stages and continuous EEG analysis. EEG data collected by the PowerSleep device can be transferred to the computer by a technician after use and used to assess sleep quality. Soft audio tones (below 65dB to prevent arousals from sleep) will be administered via the speakers during deep sleep throughout the night.

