- Individuals who self-report a history of recurrent seizures or epilepsy or family history of hereditary epilepsy or have a history of medical conditions that could increase the chance of seizures (e.g. stroke, aneurysm, brain surgery, structural brain lesion).
- Individuals who self-report severe contact dermatitis or allergy to silver.
- Individuals who self-report moderate hearing loss.
- Inability to achieve appropriate headband fit (for prototype 1).
- Planned air travel or travel across more than one time zone during the anticipated period of the study with PowerSleep or PLL device use.
- Alpha-delta sleep on the first night in the sleep lab.
- Intentional naps during the work week.

Classes of medications that will not be allowed include:

Class	Examples
Sedating Antihistamines	chlorpheniramine, brompheniramine, diphenhydramine, doxylamine
OTC Decongestants	phenylephrine, ephedrine,

	pseudoephedrine
Sedative/Hypnotics	zolpidem, eszopiclone, zaleplon, ramelteon, triazolam, gabitril, tiagabine, suvorexant, gamma-hydroxybutyrate, tasimelteon
Anxiolytics	alprazolam, clonazepam, diazepam, lorazepam
Sedating Antidepressants	amitriptyline, nortriptyline, duloxetine, venlafaxine, mirtazapine, nefazodone, buspirone, bupropion
Medications for Attention Deficit Hyperactivity Disorder	atomoxetine, methylphenidate, amphetamine
Stimulants	amphetamine, modafinil, armodafinil
Dopamine Agonists	ropinirole, pramipexole, rotigotine
Narcotic/Opioid Analgesics	Including tramadol
Dextromethorphan	Many OTC cough products
Dietary supplements and other preparations affecting sleep-wake regulation	Kava (Piper methysticum), Ashwagandha (Withania somnifera), Valerian (Valeriana officinalis), St. Johns Wort (Hypericum Perforatum)
OTC stimulants	
Diet aids	
Melatonin	

*Participants who are on a stable and well-tolerated pharmacological treatment for hypertension, dyslipidemia, or thyroid replacement will not be excluded as long as they continue to take their medication at the same dose and at the same time(s) of day

IV. STUDY PROCEDURES AND MEASUREMENTS

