Each subject will undergo a baseline screening period with screening questionnaires, clinical history, and 1 week of actigraphy measurement to determine eligibility for inclusion in the study. Prior to the overnight study they will undergo an additional 1 week of actigraphy measurement. Each subject will have two 3 day/2 night stays, separated by one week. Including outpatient screening and the inpatient study periods, the duration of participation for each subject will be ~5 weeks. We anticipate 6 months to enroll and complete the 12 subjects. Primary data analysis should be completed within one year of starting this study.

Study Procedures:

Participants may be screened over the phone to determine eligibility. A screening script will include a general review of key inclusion and exclusion criteria, and the Stop-Bang Questionnaire to assess risk for undiagnosed obstructive sleep apnea. Participants that meet all eligibility criteria will be asked to come into the research lab for a brief daytime screening visit. Participants who are interested and eligible will be consented. Participants will be provided with information on use of the actigraph and sleep logs at

home. Participants will be asked to return their actigraph and sleep logs to the laboratory either in person or via pre-paid FedEx. Participant qualification will be assessed based on sleep logs and the actigraph results. Qualifying participants will wear the actigraph and fill out sleep logs again for the week prior to their first overnight visit.

[figure not shown]

Figure 1. Overall Study Design. Qualifying participants will be randomized to receive either stimulation or sham condition. Then each group will be further randomized to receive PowerSleep Prototype 1 or Prototype 2 system at their first overnight visit, and will receive the other condition at their second overnight visit. Overnight visits will have a one night washout in between nights. The overnight visits (Visits 3 and 4) are scheduled as two sets of 3 day/2 night overnight studies and may be completed with a washout period of 5- 14 days between visits. In order to assess sleep quality, participants with an arousal index (AI) > 20 events/hour or alpha-delta sleep during an overnight visit will be excluded from further participation in the study. On the morning following each treatment, the participants will remain the lab to complete daytime function assessments and questionnaires.

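### The arousal-index and alpha-delta removal rule acts on randomised nights; analysing completers only, with no sensitivity analysis, discards recorded active/sham pairs and may select participants by condition

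*Combined protocol and SAP*

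**What the plan says.** **The rule.** The Figure 1 caption (section IV, Study Procedures and Measurements) states that participants with an "arousal index (AI) > 20 events/hour or alpha-delta sleep during an overnight visit will be excluded from further participation". It also defines the visits concerned: "The overnight visits (Visits 3 and 4) are scheduled as two sets of 3 day/2 night overnight studies". The Exclusion Criteria carry a narrower item, "Alpha-delta sleep on the first night in the sleep lab", which does not mention the arousal index (AI).

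**What those nights are.** Under Visit 2 Procedures, "Participants will be randomly assigned to the sham or active stimulation condition during the first night of the overnight visits", with the other condition on the second night. Visit 4 repeats the layout with the other prototype. Screening consists of questionnaires, history and actigraphy.

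**What is analysed.** Section V (General Considerations; Primary Efficacy Analysis) limits efficacy to participants who finish all four nights and have SWA data in all four conditions. Daytime outcomes use the same model. Only safety covers everyone randomised. Sensitivity analysis is ruled out. Section VI (Withdrawal Criteria) provides for replacing participants who withdraw, until ten have complete data.

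**Tones and arousal.** Visit 2 Procedures specifies "Soft audio tones (below 65dB to prevent arousals from sleep". The Prototype 2 definition says an "audible soft volume that do not result in arousals will be used". Section I describes Prototype 1 as giving "acoustic stimuli that are calibrated to stimulate SWA without awakening the user". Section VI (Potential risks) nevertheless accepts that stimulation may fragment sleep, although this is not intended, and provides for halting the tones if sleep is significantly disturbed.

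**The concern.** A criterion measured under treatment decides who stays, and the efficacy analysis then drops everyone who did not stay. Two separate consequences follow.

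1. **Lost data.** A participant removed after the first stay has already supplied one active and one sham night on the same prototype. That pair is a valid within-person comparison, and the completer set throws it away. With a target of ten, each pair counts.
2. **Possible selection.** If tones raise the AI in some people, removals will be more common after active nights. If those people also respond differently in SWA, the completers no longer represent those randomised. Overnight monitoring (section IV) plays tones in N3 for Prototype 1 but in N2 or N3 for Prototype 2, so removals could also differ between the two devices being compared.

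Replacing withdrawals would restore the number of participants, not the randomised set. The plan does intend to list reasons for discontinuation by treatment group. Since every participant is assigned all four conditions, that listing may not show which night triggered the removal.

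**Working it through.** **Plan's own figure.** Section V enrols 12 to obtain 10 complete data sets: 1 − 10/12 = 16.7% loss. No loss rate is stated, and none is given for AI > 20.

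**SD of the active-minus-sham SWA change.** The only source is the in-lab study in section I: "18/24 75% (> 0% increase), 15/24 62.5% (> 5% increase". If changes are normal, 75% above 0 and 62.5% above 5 give SD = 5/(0.674 − 0.319), about 14 points. This is imprecise: a profile likelihood on the counts 6/3/15 gives an 80% interval of 8 to 31. Bias and standard error both scale with SD, so their ratio does not depend on it.

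**Assumptions (not in the documents).** No true effect; same active/sham order in both stays; a night-4 trigger does not remove anyone; correlation 0.5 between triggering and low SWA on that night. Trigger rates per night are 6% active and 6% sham (equal), or 11.5% active and 0% sham (active only).

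**Share removed, acting night by night on nights 1–3.**
- Equal: 1 − 0.94³ = 16.9%.
- Active only: active-first order 1 − 0.885² = 21.7%; sham-first order 11.5%; average 16.6%.

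**Share of those removed who have a first-stay pair.**
- Equal: (16.9 − 6.0)/16.9 = 65%.
- Active only: (16.6 − 5.75)/16.6 = 65%.
- If removal happens only between stays: 100%, with about 12% removed.

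Per 12 randomised, the discarded pairs number 12 × 0.17 × 0.65 = 1.3 night by night, or 12 × 0.12 = 1.4 between stays. Someone removed for alpha-delta sleep on the first night has no pair.

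**Bias in the completer mean (simulation of 1,000,000 participants, SD 14, correlation 0.5, night by night).** The result depends on how much of the change variance is a stable individual response.
- All night-to-night noise: 0 with equal triggering; +0.8 with active only. If active nights trigger three times as often as sham, +0.4; if sham nights trigger three times as often, −0.4.
- Half stable response: +0.6 with equal triggering; +1.6 with active only.

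**Same active-only case, random-intercept mixed model on all recorded nights.**
- Night by night: +0.3 (all noise) and +0.9 (half stable).
- Between stays: about 0 and +0.4.

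**Scale, n = 10.** The standard error is 14/√10 = 4.4 points for one prototype. Averaged over both prototypes it is 14/√20 = 3.1 if the two differences are independent, or √(14² × 0.75/10) = 3.8 if half the variance is a shared stable response. The active-only bias is therefore 0.8/3.1 = 0.26 to 1.6/3.8 = 0.42 of a standard error.

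**The case against.** The best defence is that this is a pilot with ten completers, no sample-size calculation and low expected drop-out, in which tones are deliberately set not to arouse. No AI > 20 rate and no relation between AI and SWA is given, and any bias is smaller than sampling error. All of that stands, and it limits the point to a low-cost improvement. It does not answer the discarded pairs. Nor is the plan purely descriptive: it tests at the 0.05 level, hypothesises a gain of at least 5%, compares prototypes, and uses the daytime estimates to choose outcomes for later studies.

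The defence also has force on details. The listed discontinuation reasons do not name AI or alpha-delta sleep, so replacement of these removals is an inference. Listing by treatment group could be meant as the condition at discontinuation. The first lab night falls within an overnight visit, so the two alpha-delta statements are not strictly contradictory; what is open is whether later nights count. The first-night limit has no textual basis for AI.

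A reader might infer that the completer analysis will flatter the active condition, or that tones provoke alpha-delta sleep. The documents support neither: direction depends on which nights trigger and on an unknown relation to SWA, and nothing in the text links tones to alpha-delta sleep.

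**Conclusion.** The structure is established from the text: a post-randomisation removal rule, a four-night completer set for efficacy, and no sensitivity analysis. The loss of recorded pairs follows whenever someone is removed after finishing the first stay. Dependence of AI-based removal on condition, and possibly on prototype, is plausible from the protocol's own risk statement but not shown.

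The bias figures are illustrations resting on assumed trigger rates, correlation and variance split. Two tempting readings go too far. Equal triggering on active and sham nights does not guarantee zero bias: it does so only without a stable individual response. And a mixed model reduces the bias without removing it. Worth fixing because the change is cheap, not because the likely bias is large.

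**What to change.** 1. **Primary model.** Analyse all randomised participants with at least one usable night in a mixed model: participant random effect; therapy, prototype, their interaction and period as fixed effects; a small-sample degrees-of-freedom method such as Kenward-Roger. Report the four-night completer RMANOVA alongside.
2. **Reporting.** Tabulate AI by condition and prototype, and removals by the condition and prototype of the triggering night.
3. **Sensitivity analysis.** Replace the sentence ruling it out with one analysis that sets the active-sham difference to zero for participants removed under this rule who have no recorded pair. For scale, ten completers plus two such participants give 10/12 = 0.83 of the completer mean.
4. **Reconcile the Exclusion Criteria with the Figure 1 caption.** State whether alpha-delta sleep counts on the first night only or also later, whether the caption's rule acts after each night or each stay, and whether someone who first meets it on night 4 is a completer. No threshold or clinical rule is proposed here.

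Cost: SAP wording, one table and slightly more analysis; no added participants or nights. The estimate may be less favourable, and some bias may remain.
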